12.4 PARTICIPANT AND DATA CONFIDENTIALITY19

CONFIDENTIAL

This material is the property of the NYU School of Medicine and Langone Medical Center. Do not disclose or use except as authorized in writing by the study sponsor

13	DATA HANDLING AND RECORD KEEPING	19
13.1	DATA COLLECTION AND MANAGEMENT RESPONSIBILITIES	19
13.2	STUDY RECORDS RETENTION.....	19
13.3	PROTOCOL DEVIATIONS	19
13.4	PUBLICATION AND DATA SHARING POLICY	20
14	STUDY FINANCES.....	20
14.1	COSTS TO THE PARTICIPANT	20
14.2	PARTICIPANT REIMBURSEMENTS OR PAYMENTS.....	20
15	CONFLICT OF INTEREST POLICY.....	20
16	ATTACHMENTS	21

CONFIDENTIAL

List of Abbreviations

AE	Adverse Event/Adverse Experience
HIPAA	Health Insurance Portability and Accountability Act
ICF	Informed Consent Form
IRB	Institutional Review Board
PI	Principal Investigator
VR	Virtual Reality
PwMS	People with Multiple Sclerosis

CONFIDENTIAL

Protocol Summary

[figure not shown]
Title	Virtual Reality (VR) to improve Quality of Life in Patients diagnosed with Neurological Disorders
Short Title	VR to improve Quality of Life
Brief Summary	Participants with neurological disorders will be recruited to complete sessions of virtual reality (VR) immersion. VR has been shown to have therapeutic benefit in certain patient populations and requires further clinical study to determine the extent to which VR can be used to rehabilitate and reduce symptom burden. This study seeks to pilot newly developed VR methods and collect preliminary data in order to support research grants and inform larger clinical trials. This proposed study will explore the tolerability and preliminary efficacy of Virtual Reality (VR), specifically to determine whether VR can acutely reduce the severity of symptom burden caused by neurological disorders. Additionally, a second group of MS participants with clinically significant pain will be recruited to test the analgesic effects of VR.
Phase	N/A
Objectives	Specific Aim 1: To test the feasibility and tolerability of immersive VR therapy in patients with neurological disorders. Specific Aim 2: To measure the efficacy of a VR program to manage chronic pain for people with multiple sclerosis.
Methodology	Study Group 1: Open-Label Study Group 2: Single blinded, randomized treatment allocation to one of two VR treatment conditions
Endpoint	Completion of up to twelve one-hour sessions of VR alongside study measures taken at the end of the last completed session

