5.2 Eligibility for MS patients with Chronic Pain

We will include participants who experience pain as a symptom of their MS. Exclusion criteria will include any health condition contraindicated with the use of a VR device (including uncontrolled epilepsy, vertigo, inability to balance, subpar visual and motor skills). See table 2 for full eligibility criteria

Inclusion Criteria	Exclusion Criteria

 • 18-79 years of age • Has been diagnosed by a clinician as having MS • Able to commit to the designated period of testing • Able to understand the informed consent process and provide consent to participate in the study • Capacity to complete study procedures as determined by screening personnel • A Brief Pain Inventory interference score of at least 3 or more. • SDMT Z-Score > -3.0 • WRAT4 Standard Score > or = 85 	
 • Visual, auditory, and motor deficits that would prevent full ability to understand study • Visual, auditory, and motor deficits that would prevent full ability to operate VR equipment • Uncontrolled epilepsy • Current diagnosis of vertigo • Uncontrolled mood disorders • History of Psychosis or Schizophrenia • EDSS Score greater than 6.5 • Unable to tolerate or manipulate VR treatment procedures (as evidenced by VR capability assessment)

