5.7 Participant Withdrawal or Termination

Participants may withdraw from the study at any point for any reason.

Should a participant feel any adverse event such as nausea at any point during the VR sessions, the headset will be removed and the session will be paused. The participant will be asked to rate their adverse event, nausea for this example, on a 1-10 likert scale, 1 being mild and 10 being the need to vomit. If the participant rates their nausea at a level of 7 or more or expresses the need to vomit the session will be ended for that day. If the participant rates the nausea below a 7 and expresses the desire to continue, then the study personnel will wait with the participant (for up to 5 minutes) until the nausea is resolved and will then resume the VR session. Should the participant experience nausea a second time in the same session then the headset will be removed and that day's VR session will be ended (see Figure 1).

The participant's participation in the study will be terminated if two VR sessions are cancelled due to nausea or if participants express the desire to stop.

Figure 1. Visual representation of study stop criteria

6 Study Device

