7.1 Study Procedures/Evaluations

Participants will complete an informed consent form before any study procedures begin. Participants under the age of 18 will complete an assent form while their legal parent or guardian will complete a consent form.

Participants will complete relevant assessments listed in [Table 2](#) before undergoing a VR session.

Participants may complete as much as one hour of VR therapy during any given session.

Study Group 1: There may be as many as twelve VR sessions during the course of the study. Study personnel will be available to guide participants during the entire duration of the VR session and ensure each session is completed safely. VR treatment will entail use of computer software designed to immerse participants and engage them in exercises. Software includes virtual painting, walking through vivid and calming settings, solving puzzles, among others.

Study Group 2: Similar to study group 1, study personnel will be available to guide participants throughout each VR session. VR treatment will be identical to study group 1.

Participants with MS will only be able to receive eight treatment sessions in this study group and will complete their treatment over four weeks.

Two treatments sessions must be completed each week (of the four weeks) and separated by at least one day. For example, if a participant completes one of their weekly treatments on Monday, they are not able to complete the treatment on Tuesday but may come in on any of the remaining weekdays that study staff are available.

Participants will attend a baseline visit with assessment and training procedures and receive their first treatment immediately after all baseline assessments. Participants will then complete the remaining seven treatment sessions over four weeks. At the final treatment session, participants will repeat assessments. One week following the final treatment session, participants will be asked to return to clinic to complete assessments once more to test cumulative benefits one week following treatment end.

CONFIDENTIAL

This material is the property of the NYU School of Medicine and Langone Medical Center. Do not disclose or use except as authorized in writing by the study sponsor

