We will submit data safety monitoring reports to the IRB after 10 participants are enrolled, and follow with reports for each further increment of 10 active enrollees. The study PI will review data safety reports in order to assess whether AE incidence rate is on par with that in publisher literature[19]. The research coordinator will submit data safety monitoring reports reviewed and signed by the PI. Any adverse effects, such as feelings of nausea, will be catalogued and quantified to determine rates of incidence. If the rates of incidence are higher than previously expected by PI based on literature then the study will be placed on hold and assessed. The most common adverse event expected is motion sickness and nausea, of which estimates of incidence vary across studies as technology has advanced and varied greatly over the last 20 years (some studies report 97% of participants as reporting none to mild nausea[19]). We conservatively expect a 20% incidence rate for feelings of motion sickness or nausea. We also expect other adverse event incidence rates such as headache, vertigo, and seizures to be exceptionally low, below 5% of occurrence.

9 Statistical Considerations

Study Group 1: As this is an exploratory protocol that is collecting data for future power analyses, the designation of recruiting 60 human subjects is somewhat arbitrary. Following the results and any benefit experienced by these initial participants, future clinical trials can be conducted with properly powered samples. Recruitment of 60 participants would allow for enough data for a sufficient power calculation for future trials to determine clinical efficacy.

Preliminary paired sample t-tests will be conducted to determine whether participants experienced statistically significant change in neurological disorder symptoms.

General means and standard deviations will be reported and analyses will inform future power analyses of clinical trials that will use VR as a treatment modality.

Study Group 2: The second pool of participants will be n=44, following preliminary effect size analyses. Participants who complete at least 6 of the 8 (75%) total sessions will be included in analyses, and we have anticipated a dropout rate of up to 10%, resulting in 20 or more completers in each group.

CONFIDENTIAL

This material is the property of the NYU School of Medicine and Langone Medical Center. Do not disclose or use except as authorized in writing by the study sponsor

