Primary outcome will be the change in PROMIS Pain interference from baseline to the study end visit. Based on a previous, successful clinical trial in chronic pain also using an 8-session nonpharmacologic intervention[20], we can expect to have 89% power to detect a significant group difference between the two study conditions. We will also compare change between the groups from baseline to treatment end on the additional self-report measures.

Secondary outcomes will be change in pain visual analog scales completed before and after each session to evaluate acute treatment effects and changes in medication usage from baseline to treatment end measured qualitatively[21]. We will also analyze pain before and after each VR session with the Wong-Baker Faces Pain Rating Scale to compare the immediate analgesic effects of each condition and this cumulative change across sessions.

10 Source Documents and Access to Source Data/Documents

Data will be entered in the HIPAA-compliant NYU REDCap database designed specifically for this study. An anonymous database number will be assigned to each participant and will be used for both the Data Entry Sheet and the Patient Follow-up Sheets. The original consent, which includes the patient name and ID number, will be stored separately in a locked filing cabinet in a locked office. Access to this data will be restricted to study personnel only. Research data will be entered online through the secure NYU database software REDCap and source documents will be kept in a locked filing cabinet in a locked office. Participant data will be coded by the assigned ID and identifying information will not be presented or published to maintain participant privacy and confidentiality.

11 Quality Assurance and Quality Control

- Development of standard protocols to perform all data collection and follow-up activities.
- Use of standardized forms.
- Uniform criteria for patient recruitment.
- Standardized data processing.
- Regular communications between study staff and study investigators to resolve questions.
- Performance monitoring of data collection and data processing activities, as well as preparation of periodic reports and analyses on performance monitoring.
- Monthly monitoring of recruitment statistics.

12 Ethics/Protection of Human Subjects

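### The randomised Group 2 comparison is restricted to participants who complete at least 6 of 8 sessions, and no all-randomised analysis is stated

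*Combined protocol and SAP*

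**What the plan says.** The Methodology row of the Protocol Summary describes Group 2 as "Single blinded, randomized treatment allocation to one of two VR treatment conditions". Section 6.1.1 describes the two catalogues: one interactive, one of videos that are only watched.

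Section 9 sets the Group 2 sample at 44 and gives a single analysis set: "Participants who complete at least 6 of the 8 (75%) total sessions will be included in analyses". It allows for dropout of up to 10% and counts on at least 20 completers per group. It continues: "Primary outcome will be the change in PROMIS Pain interference from baseline to the study end visit", and "we can expect to have 89% power to detect a significant group difference between the two study conditions".

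Section 5.7 gives two routes out of treatment: "The participant's participation in the study will be terminated if two VR sessions are cancelled due to nausea", and "Participants may withdraw from the study at any point for any reason". Section 5.2 excludes people who fail a VR capability assessment at entry.

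The primary outcome is measured at the visit described in Section 7.1: "One week following the final treatment session, participants will be asked to return to clinic to complete assessments once more".

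Nowhere do the documents name an intention-to-treat or all-randomised set, a sensitivity analysis or a method for missing outcomes.

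**The concern.** Randomisation makes the two arms comparable at the moment of allocation. A filter applied later keeps that property only if it removes similar people from both arms. Completing six sessions is known only after allocation, and the allocated content can influence it. Interactive and passive content may be tolerated differently over eight sessions. One catalogue may hold interest better, and a participant who feels no benefit may withdraw. The demanding schedule of two sessions a week adds further losses.

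The rule also goes beyond unavoidable missing data. A participant who completes five sessions and attends the study-end visit has an observed primary outcome, yet is left out.

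Section 4.1 says Group 2 is to establish efficacy in chronic MS pain. Under this rule a difference between catalogues could reflect who stayed instead of what the catalogue does. If those excluded would have done worse, the arm that loses more people looks better. If exclusions are balanced and alike in kind, there is little or no bias. No reporting of exclusions by arm is planned, so a reader could not tell which case applies.

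**Working it through.** **1. The plan's own figure.** From Section 9: n = 44, dropout 10%. 44 × (1 − 0.10) = 39.6, or 19.8 per arm. This agrees with the stated 20 per group to within rounding. The sample size is thus built on completers. The allocation ratio is not stated; 22 per arm assumes 1:1, which the 20 per group implies.

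**2. Size of the possible bias (illustration; none of these assumptions comes from the documents).** Assume no true difference between catalogues and 22 per arm. Each participant has a latent propensity L to be excluded, standard normal, with correlation ρ to a worse pain change. A fraction p is excluded when L exceeds z, the (1 − p) normal quantile. Then, in SD units:

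- improvement in the mean of those retained = ρ·φ(z)/(1 − p)
- gap between excluded and retained = ρ·φ(z)/[p(1 − p)]

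For p = 0.15, φ(z)/(1 − p) = 0.2332/0.85 = 0.274. For p = 0.05 it is 0.1031/0.95 = 0.109. For p = 0.30 it is 0.3477/0.70 = 0.497. The bias is ρ times the difference between arms; for 15% v 5% at ρ = 0.5 it is 0.5 × (0.274 − 0.109) = 0.083. Type I error is from 100,000 simulated two-sample t-tests at a nominal two-sided 5%.

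| Exclusion by arm | ρ = 0.3 | ρ = 0.5 | ρ = 0.7 |
|---|---|---|---|
| 10% v 10% | 0 SD; 5% | 0 SD; 5% | 0 SD; 5% |
| 15% v 5% (average 10%, as planned) | 0.05 SD; 5.2% | 0.08 SD; 5.8% | 0.12 SD; 6.7% |
| 30% v 5% (average 17.5%, beyond the plan) | 0.12 SD; 6.3% | 0.19 SD; 9% | 0.27 SD; 13% |

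The implied gap between excluded and retained participants, for p between 5% and 30%, is about 0.5 to 0.65 SD at ρ = 0.3, and 0.8 to 1.5 SD across ρ = 0.5 to 0.7.

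**3. Cross-check with whole participants.** Let those excluded be s SD worse than their arm's overall mean. Completers then look better by e·s/(1 − e), where e is the fraction excluded.

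- 4 of 22 v 0 of 22: for s = 0.5, (4/22 × 0.5)/(18/22) = 0.11 SD; for s = 1.0, 0.22 SD. Type I error 6.3% and 10.5%.
- 3 v 1: 0.06 and 0.11 SD. Type I error 5.3% and 6.3%.
- 2 v 2: no bias.

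**4. Power of an all-randomised analysis.** The documents give no effect size, SD, significance level or sidedness for the 89%, so it cannot be reproduced. Assuming a two-sided 5% t-test, 89% at 20 per arm implies a standardised effect d of 1.03. With outcomes on all 22 per arm:

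- full effect (d = 1.03): 92%
- 10% gain nothing (0.9 × 1.034 = 0.93): 85%
- 20% gain nothing (0.8 × 1.034 = 0.83): 76%

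Non-responders also widen the spread in their arm. With that extra variance counted, the last two become 84% and 73%.

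**The case against.** The strongest case is that little may be at stake. The protocol describes itself as piloting methods and gathering preliminary data. At its own dropout figure the distortion is small, and nothing says the catalogues differ in tolerability. Participants are screened for VR capability and blinded to catalogue. Milder nausea can lead only to a pause, and two cancellations do not always breach the rule: if they are sessions 7 and 8, six are already complete. The larger biases above need excluded participants to do much worse than the rest, for which the documents give no evidence.

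Most of this stands as a limit on size. It does not restore the randomised comparison. The pilot label sits poorly with a group meant to establish efficacy at 89% power, and the 10% is an expectation, not a ceiling.

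A second objection is that some assessment of people who stop is foreseen. The Protocol Summary places study measures at the end of the last completed session. Section 5.5 repeats baseline measures if the first session turns out to be the last. Table 3 marks pain measures at treatment sessions. These would yield useful data. However, they do not supply the study-end outcome one week after treatment for someone terminated early, and no analysis of such people is planned.

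The word only does not appear in the analysis-set sentence. Since the same sentence counts completers per group and no other set is named, the restrictive reading is the natural one.

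**Conclusion.** The concern holds. The sole analysis set stated for the trial's only randomised comparison is chosen by a post-randomisation event that allocation can affect, and it can discard observed outcomes. This needs correcting before outcome data are seen, because uncollected assessments cannot be recovered and a set chosen afterwards would lack credibility.

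The actual bias is unknown in size and direction. Under the illustrative selection model it is nil with balanced exclusion and 0.05 to 0.12 SD at 15% v 5%. It reaches 0.12 to 0.27 SD only at an imbalance beyond the planned dropout. The finding rests on the design defect; those figures show that it may prove minor in practice.

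**What to change.** - **Primary set.** In Section 9, make the primary Group 2 analysis all randomised participants, as allocated, whatever number of sessions they complete.
- **Follow-up.** Leave the rule for stopping VR as it is, but in Sections 5.7 and 7.1 separate stopping VR from leaving the study. Ask those who stop for the PROMIS pain measures at treatment end and study end, timed from their first session.
- **Missing outcomes.** State a method. One option is a likelihood-based repeated-measures model of the treatment-end and study-end scores with baseline as covariate. Add a missing-not-at-random sensitivity analysis, for example shifting imputed scores by arm until the conclusion changes. The particular methods are examples; stating them in advance is the requirement.
- **6-of-8 set.** Keep it as a sensitivity analysis, define a completed session, and report exclusions by arm with reasons.
- **Power.** Restate the 89% for the all-randomised set, with its effect size, SD and test.

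The cost is wording in three sections and two short assessments for about 4 of 44 participants at 10% dropout (44 × 0.10 = 4.4). Since Section 7.1 has participants return to the clinic, and Section 5.7 currently ends participation, some extra visits and a consent change may be needed. The main statistical cost is dilution: under the back-solved effect, power is 85% or 84% (without or with the extra variance) if 10% gain nothing, and 76% or 73% if 20% gain nothing.

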4.1 Description of Study Design

Study Group 1 (Neurological Disorders):

The study is intended as a pilot trial for VR in neurological conditions. An open-label design will be implemented. Once participants are found eligible, they will complete one full session of VR using a headset preconfigured by study personnel. Participants will complete up to twelve sessions of VR therapy that may extend as long as an hour in length. Total number of study visits will be up to the study personnel's discretion. Study personnel will guide VR headset placement and program assignment (i.e., interactive or passive catalogues).

Study Group 2 (Chronic Pain in MS): The study will include an arm for people with MS (PwMS) and chronic pain. We will determine the efficacy of VR for the management of chronic pain in PwMS. Participants in this study group will receive eight treatment sessions over four weeks. Participants will be blinded to the VR treatment catalogue they receive.

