4.2.2 Study Group 2 (Chronic Pain in MS): Study Endpoints

Primary study endpoint will be change in the Patient Reported Outcomes Measurement Information System (PROMIS) pain intensity and interference measures administered at baseline, treatment end, and study end.

Secondary outcomes will include additional measures of pain and other symptoms (i.e. mood and fatigue). We will also measure the acute effects of the treatment on pain before and after each VR session.

5 Study Enrollment and Withdrawal

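### The randomized Group 2 comparison of change in PROMIS Pain Interference names no model or baseline covariate; ANCOVA on baseline would usually be modestly more precise at little cost

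*Combined protocol and SAP*

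**What the plan says.** The Protocol Summary describes Group 2 as "Single blinded, randomized treatment allocation to one of two VR treatment conditions"; it is the only randomized comparison in the study. Section 4.1 gives its purpose: "We will determine the efficacy of VR for the management of chronic pain in PwMS".

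Section 4.2.2 puts the primary endpoint on PROMIS "pain intensity and interference measures administered at baseline, treatment end, and study end". Section 9 narrows this: "Primary outcome will be the change in PROMIS Pain interference from baseline to the study end visit". It then says "we can expect to have 89% power to detect a significant group difference between the two study conditions", and for the remaining scales: "We will also compare change between the groups from baseline to treatment end on the additional self-report measures". Analysis is limited to participants completing at least 6 of the 8 sessions, with up to 10% dropout among 44 enrolled, "resulting in 20 or more completers in each group".

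No test, model, covariate or confidence interval is named for any between-arm comparison. The only named tests are paired t-tests, in Section 3 (Specific Aim 2) and in Section 9 under Study Group 1. Both are before-after tests within a cohort and cannot compare arms.

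**The concern.** Section 9 gives the primary comparison an outcome and a power figure but no method. Comparing change between groups, with nothing further said, would ordinarily be done as a two-sample comparison of change scores. That fixes the coefficient on baseline at 1. ANCOVA estimates the coefficient from the data, and when the true slope is below 1 the change score carries avoidable noise from baseline.

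With about 20 analysed per arm, a few percent off the standard error is worth a sentence. Naming the model in advance also means that nobody has to choose between adjusted and unadjusted results after seeing the data.

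**Working it through.** **Inputs from the documents.** 44 enrolled and 10% dropout give 44 × 0.9 = 39.6, or 19.8 per arm, which agrees with the plan's 20. I use n = 20 per arm.

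**Inputs not in the documents (assumed).** The baseline-to-follow-up correlation ρ, shown from 0.5 to 0.9; and k, the follow-up SD divided by the baseline SD, first 1 and then varied.

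**The plan's own figure.** The 89% power cannot be reproduced, because alpha, effect size and SD are not given. For a two-sided 5% t-test with 20 per arm (38 df), it corresponds to a standardized difference of 1.034.

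**Equal SDs.** With common SD σ, the per-person variance of a change score is 2σ²(1−ρ). The ANCOVA residual variance is σ²(1−ρ²). Their ratio is (1+ρ)/2. Estimating the slope multiplies the expected ANCOVA variance by 1 + 1/(2n−4) = 1 + 1/36 = 1.0278. At ρ = 0.7 this gives 0.85 × 1.0278 = 0.874.

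| ρ | Variance ratio, ANCOVA/change | Variance saving | SE ratio | Power, if 89% is for an unadjusted two-sided change-score test |
|---|---|---|---|---|
| 0.5 | 0.771 | 23% | 0.878 | 95.2% |
| 0.6 | 0.822 | 18% | 0.907 | 94.0% |
| 0.7 | 0.874 | 13% | 0.935 | 92.6% |
| 0.8 | 0.925 | 7.5% | 0.962 | 91.2% |
| 0.9 | 0.976 | 2% | 0.988 | 89.7% |

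The power column divides the noncentrality 1.034 × √10 by the SE ratio and uses 37 df. In a simulation of 4,000 trials per value at 20 per arm, mean 95% CI width ratios were 0.880, 0.935, 0.962 and 0.989 at ρ = 0.5, 0.7, 0.8 and 0.9. ANCOVA gave the narrower interval in 96%, 85%, 73% and 51% of trials.

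**Unequal SDs.** The expected ratio becomes 1.0278 × k²(1−ρ²)/(1 + k² − 2kρ).

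- At k = 1.15 and ρ = 0.7: 1.0278 × (1.3225 × 0.51)/(2.3225 − 1.61) = 0.973, a 2.7% saving. At ρ = 0.5 the saving is 13%; at ρ = 0.8 there is a 1.4% loss.
- At k = 0.9 the savings at ρ = 0.5, 0.7 and 0.8 are 31%, 23% and 19%.
- The gain reaches zero at k of about 1.55, 1.36, 1.22, 1.11 and 1.03 for ρ = 0.5 to 0.9.
- The least favourable case is k = 1/ρ, where the slope is exactly 1 and the ratio is 1.0278. Conditional power there is about 88.1%.

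**Could entry selection push k above 1?** Section 5.2 requires "A Brief Pain Inventory interference score of at least 3 or more", which can narrow baseline spread. Assume normal scores, a correlation of 0.7 between that scale and PROMIS Pain Interference, half the source population qualifying, and follow-up depending on baseline PROMIS only. Baseline variance falls to 1 − 0.49 × 0.6366 = 0.688. At a pre-selection ρ of 0.7, change-score variance is 0.09 × 0.688 + 0.51 = 0.572 and ANCOVA variance is 0.51. The ratio is 1.0278 × 0.51/0.572 = 0.916, a saving of about 8% instead of 13%. At pre-selection ρ of 0.5, 0.8 and 0.9 the savings are about 16%, 4.5% and 1%.

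**Penalty in a single trial.** The factor 1.0278 is an average. For a given trial it is 1 + t²/38, where t is the two-sample t statistic for the baseline difference. It exceeds 1.0278 in about 31% of trials. Its 95th percentile is 1 + 2.024²/38 = 1.11.

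**The case against.** The strongest reply is that Section 9 fixes an outcome, not a test. ANCOVA on change is compatible with every sentence in it, so the inefficient comparator is inferred. That stands: what is documented is that no method is named, and the precision loss arises only if an unadjusted test would in fact be run. But the silence leaves both options open, and one sentence settles it.

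Second, the size of the gain rests entirely on assumed ρ and k. That also stands. At ρ = 0.9 with equal SDs, ANCOVA is narrower in only about half of trials, so the word usually refers to moderate correlations. In expectation, however, the trade is lopsided: savings of 13% to 23% for ρ of 0.5 to 0.7 with equal SDs, against a loss of at most 2.8%.

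Third, any single pre-specified model would remove the choice after the data are seen. True; the specific case for ANCOVA is precision.

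Three stronger readings are tempting, and the documents do not support them. A reader might infer that comparing change scores biases the result; in a randomized comparison it does not, and no error-rate failure is shown. A reader might infer the reverse, that randomization guarantees either analysis; it does not, because completing 6 of 8 sessions is determined after randomization. And a reader might take 2.8% as a ceiling on the penalty in every trial; it limits the expected variance only.

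**Conclusion.** The point holds as a modest improvement in precision and pre-specification for the study's only randomized comparison. At 20 per arm with equal SDs, ANCOVA lowers the expected variance by about 23% at ρ = 0.5, 13% at 0.7, 7.5% at 0.8 and 2% at 0.9. The gain shrinks as ρ rises and can disappear or slightly reverse if the follow-up SD is sufficiently larger than the baseline SD. All of this assumes that the unnamed comparison would be unadjusted.

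The stated 89% power is neither confirmed nor contradicted. ANCOVA would not supply its missing inputs, repair the completer-only analysis set, or resolve the difference between Section 4.2.2 (intensity and interference) and Section 9 (interference only). The change should be made, but the trial does not stand or fall on it.

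**What to change.** Add to Section 9, Study Group 2, text such as:

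> PROMIS Pain Interference at study end (or, equivalently, its change from baseline) will be compared between arms by ANCOVA with baseline PROMIS Pain Interference as covariate. The adjusted difference and its 95% CI will be reported. PROMIS pain intensity and the other self-report measures will be analysed in the same form, each with its own baseline value as covariate.

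The two forms of the outcome give the same adjusted treatment estimate and interval once baseline is in the model, so the outcome definition need not change.

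The cost is one degree of freedom per model, a small average variance penalty in unfavourable cases, and a short amendment that needs IRB approval before use (Section 12.2). No data are added beyond what a change outcome needs, and Section 4.2.2 schedules the baseline measure. The same amendment could add the PROMIS pain measures to the Section 7.2 table, whose PROMIS row covers fatigue, mood and health-related quality of life but does not mention pain.
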